5.5 Output for WP3

Output: An overview of resuscitation practice and compliance with the current ROLE guideline in England and Wales and an assessment of the potential impact of alternate termination of resuscitation rules.

6. EXPERIENCES OF AND PERSPECTIVES ON PRE-HOSPITAL TERMINATION OF RESUSCITATION (WP4)

6.1 Study design for WP4

Aim: Explore the perspectives of patients, relatives, paramedics and emergency medicine staff and consider the ethical aspects of termination of resuscitation rules.

Objectives:

- Understand the experiences of those impacted by decisions concerning out of hospital termination of resuscitation
- Identify the challenges for paramedics faced with out of hospital termination of resuscitation decisions

- Explore the values, beliefs and preferences of cardiac arrest survivors, families, paramedics and emergency medicine staff concerning out of hospital termination of resuscitation.
- Identify the ethical considerations related to out of hospital termination of resuscitation decisions.

Plan of investigation: We will undertake semi-structured interviews with three distinct groups:

- Survivors of cardiac arrest/relatives of survivors and non-survivors
- Ambulance staff
- Emergency medicine staff

Setting: Up to three ambulance services and two Emergency Departments (EDs) within the area covered by each service. Within each participating ambulance service, we will identify a busy urban ED and a less busy rural/suburban ED.

PPI and study advisory group involvement:

Early in the study the PPI and study advisory group will work with the project team to develop vignettes for use in the interviews. These will represent common and more unusual cardiac arrest scenarios where a decision to continue/not continue resuscitation was made. During data analysis we will engage these groups with interpretation of our data and seek their advice on presentation of data for dissemination.

Recruitment:

We will visit ambulance services who express an interest in participating in the qualitative study. In collaboration with our ambulance service partners we will identify EDs that could be potential collaborators. We will approach the lead doctor and / or nurse of the identified EDs and arrange to visit the department to explain the study. We will provide potential collaborating EDs with information about the study for them to share with staff likely to care for patients who have suffered an out of hospital cardiac arrest. In each organisation that expresses an interest to participate we will secure the necessary approvals via their respective Research and Development Department.

Ambulance staff:

Participating ambulance services will identify individual cardiac arrest cases where ROLE is performed and patients do not get transported to hospital. Paramedics who performed ROLE will be identified by the research paramedic, as soon after the event as practicable, and invited to participate in the study via their work email from the Ambulance Service PI (or their delegate). The email/letter of invitation will include information about the study. Paramedics interested in the study will be asked to contact the research team to discuss the study and arrange an interview. Verbal consent to retain contact details will be confirmed when an interview is scheduled. A study information sheet will be posted/emailed to the potential participant prior to the interview. Formal consent will be obtained on the day of the interview before the interview starts. Consent will be written where interviews are face to face, and audio-recorded where held remotely via telephone or using an online communication platform such as Microsoft Teams. The interview will be conducted as soon as possible after the event, consent will be obtained by the research fellow prior to starting the interview.

Emergency medicine staff:

For patients suffering cardiac arrest and transferred to hospital, a hospital research nurse / local CRN nurse will contact the relevant ED the same day or the next morning to identify the member(s) of staff most involved with providing care and pass the details onto the ED PI (or their delegate) who will invite them via their work email to participate in the study. The email invitation to participate will include information about the study and a copy of the consent form. Local research staff may send one reminder. ED staff interested in the study will be asked to contact the research team to discuss the study and arrange an interview. Verbal consent to retain contact details will be confirmed when an interview is scheduled. A study information sheet will be posted/emailed to the participant prior to the interview. Formal consent will be obtained on the day of the interview before the interview starts. Consent will be written where interviews are face to face, and audio-recorded where held remotely via telephone or using an online communication platform such as Microsoft Teams. The interview will be conducted as soon as possible after the event, consent will be obtained by the research fellow prior to starting the interview.

Survivors of cardiac arrest / relatives of non-survivors:

We have experience of approaching patients and next of kin following life threatening events in our previous work (ICU decision-making,⁷⁰ PARAMEDIC2⁶⁹ and in our development of a core outcome set for cardiac arrest).⁷¹ For this study we worked closely with our PPI panel to develop the most appropriate approach to recruitment of patients and relatives, including relatives of non survivors. There is evidence that survivors of cardiac arrest and their relatives suffer significant psychological sequelae including post-traumatic stress disorder,^{72,73} with up to 50% of patients having persistent symptoms three months after the event.⁷⁴ We therefore do not plan to approach survivors or relatives until at least three months post cardiac arrest (or 3 months post death for relatives of non survivors).

For all cases where ROLE was performed on scene the research paramedic in the relevant ambulance trust will know that the patient has died. In all other cases the research paramedic will not know if the patient survived or died and so will refer to the Summary Care Record at three months post event. The research paramedic will pass this information to the Ambulance Service PI (or their delegate).

The Ambulance Service PI (of their delegate) will write to survivors and relatives of non survivors with very brief information about the study asking if they (or a family member) would be prepared to take part in the study. One reminder invitation may be sent approx. 4-6 weeks after the initial invitation. Those interested in the study will be asked to contact the research team who will arrange a telephone conversation with the researcher. The researcher will discuss the study in more detail answering any questions raised by the potential participant. Where the participant confirms they are willing to be interviewed verbal consent to retain contact details will be confirmed and an interview scheduled at a mutually convenient time and location. Prior to the interview a more detailed information sheet will be posted/emailed to the participant. Formal consent will be obtained on the day of the interview before the interview starts. Consent will be written where interviews are face to face, and audio-recorded where held remotely via telephone or using an online communication platform such as Microsoft Teams.

If the survivor agrees we will also invite a family member to be interviewed. If the survivor lacks capacity to consent their next of kin will be provided with information about the study and asked if

they will agree to be interviewed. In this situation we will ask the next of kin to sign a personal consultee form confirming that they agree that the person would not object to their relative discussing their care with the researcher for the purpose of the study. Consent will be taken immediately prior to the interview. Consent will be written where interviews are face to face, and audio-recorded where held remotely via telephone or using an online communication platform such as Microsoft Teams.

Figure 2: Recruitment of Participants

We aim to recruit the paramedics, ED staff and survivors/relatives involved in the same cardiac arrest event to allow comparison of differing perspectives of the event. However, this will not always be possible. Based on our previous experience we expect to find recruitment of survivors/relatives difficult, but that the data from those who do agree to be interviewed will be of great value to the study. If we fail to recruit patients/relatives of non-survivors, we will seek lay participants with a personal interest in heart disease by advertising through national and regional organisations, such as the British Heart Foundation, who support people affected by conditions that increase risk of cardiac arrest and peer support groups for survivors of cardiac arrest e.g. Sudden Cardiac Arrest UK. We will create a sampling frame using characteristics (age group, gender, experience of cardiac arrest) of those who express an interest in participating. For participating Acute Trusts who run a post discharge ICU clinic for patients and their families, the Trust research nurse will identify any patients attending the clinic who have survived a cardiac arrest and provide them with information about the study and contact details for the study team if they wish to learn more or participate.

Recruitment will continue until we reach data saturation. We anticipate interviewing a maximum of 60 clinical staff (30 ambulance staff and 30 ED staff) and approximately 15 patient/family participants with direct experience of the cardiac arrest event and approximately 5 family members who are not present.

The number of cardiac arrest events may be greater than 30 as not all participants will be involved in any one event.

Withdrawals and exclusions: Participants can withdraw from the study up to 14 days after their interview without prejudice. After this, the data will be undergoing analysis and it will not be possible to isolate and withdraw particular participant data.

Participants will be given contact details for the researcher who they may contact at any time after they have been recruited, until 14 days after their interview, to inform the team that they wish to withdraw consent. Their wishes will be recorded in the Study Master File using their study ID only and their data removed from the study. The researchers and the co-applicants responsible for WP4 will discuss the situation and decide whether an additional participant at that site or another site should be included. This decision will be informed by various factors including the stage of data collection at the site and the impact of the loss of data on the findings.

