6.4 Data analysis for WP4

Data quality checks: all qualitative transcriptions will be checked against the initial interview recording to ensure consistency. A record of these checks will be logged and reported back to the SMG. SMGs will also evaluate interpretations made from the data.

Data analysis: Analysis will be undertaken as follows:

- Comparative analysis of data related to cardiac events⁷⁵ Data about any one event will be grouped (although sometimes we may only have one data source for an event). From analysis of initial data we will develop an event pathway. This is likely to be before event, arrival at event, assessment, active treatment, evolving the decision to terminate or not, transport, ED activity, post ED. Data will be coded to stages in the pathway. To understand the diversity of experience and the reasons for this diversity, we will compare data from different stakeholders about the same event at the different stages and between events.
- *Thematic analysis*⁷⁶ This analysis will focus on data on expectations, dilemmas, challenges, values, attitudes, beliefs and preferences wherever it occurs in the data. Transcripts will be coded close to
text, with codes summarising the coded text. Codes will then be sorted and categorised into themes to provide a rich description of the range of perspectives and how these influence decisions and actions at cardiac events.

Descriptive ethical analysis⁷⁷ This involves interpreting and evaluating the ethical or moral dimensions
of the reality reported in the interviews. Working with our ethicist we will re-read interview
transcripts looking for explicit and implicit ethical concerns for those encountering cardiac arrest in
their work/life and the values they express or imply related to cardiac arrest. During analysis we will
relate these to current ethical, legal and professional frameworks.

Each analysis will result in a report to inform the normative ethics review and consensus conference.

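### WP4 invites paramedics only through on-scene ROLE cases and ED staff only through transferred cases, so no event can give the planned paramedic–ED or paramedic–survivor comparison

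*Protocol*

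**What the plan says.** The recruitment text in Protocol Section 6.1 gives each staff group its own index event.

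- Ambulance staff: "Participating ambulance services will identify individual cardiac arrest cases where ROLE is performed and patients do not get transported to hospital". The invitation follows from that event: "Paramedics who performed ROLE will be identified by the research paramedic, as soon after the event as practicable". The text gives no other route for ambulance staff.
- Emergency medicine staff: "For patients suffering cardiac arrest and transferred to hospital, a hospital research nurse / local CRN nurse will contact the relevant ED" to find those most involved in the care.
- Survivors and relatives are found from both kinds of event. The research paramedic knows the outcome when ROLE was performed on scene, and looks it up at three months in all other cases.

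Later in the same section the stated aim is: "We aim to recruit the paramedics, ED staff and survivors/relatives involved in the same cardiac arrest event", so that perspectives can be compared. A qualifier follows: "However, this will not always be possible". In Section 6.4, the first analysis groups data by event and codes them to a pathway running from before the event through the decision, transport, the ED and afterwards. It then says "we will compare data from different stakeholders about the same event" at each stage, and also between events.

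**The concern.** The two staff frames are defined by opposite patient dispositions, while the aim and the first analysis assume that both groups can speak about one event. Sites will follow the invitation paragraph as written, so the protocol as it stands cannot produce the linked accounts by pre-hospital and hospital clinicians that it says it wants.

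The content of the ambulance interviews is affected too. WP4 is meant to show what helps and hinders stopping on scene, and Section 1.2 lists family conflict, public location and medicolegal worry as things that limit the use of termination rules. Such barriers are likely to show most clearly in events where the crew did not stop. The index-event part of the ambulance interview is restricted to events where they did stop. The WP4 reports go to the consensus conference that drafts the new guideline.

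**Working it through.** This is a question of sampling logic, so the check is to set the frames side by side. The dispositions come from Section 1.1 (stopped in the field, transported with CPR in progress, transported after ROSC) and the frames from Section 6.1.

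| Group | ROLE on scene, not transported | Transported, CPR in progress | Transported after ROSC |
|---|---|---|---|
| Paramedic (index event) | yes | no | no |
| ED staff | no | yes | yes |
| Survivor | no | yes | yes |
| Relative of non-survivor | yes | yes | yes |

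Intersections by event:

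- Paramedic and ED staff: empty.
- Paramedic and survivor: empty.
- Paramedic, ED staff and survivor or relative: empty.
- Paramedic and relative of a non-survivor: on-scene ROLE events.
- ED staff and survivor, or ED staff and relative: transported events.

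The other recruitment routes in Section 6.1 do not change this. The post-discharge ICU clinic reaches survivors, who belong to the last two columns. Advertising through national organisations is for lay participants and adds no crews.

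The event counts point the same way.

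1. The plan's own figure is the maximum of 75 events in Section 2.3. It is reproduced by one event per interviewee: 30 ambulance + 30 ED + 15 patient or family = 75.
2. Assume one paramedic and one ED clinician per event. If the two frames overlapped fully, the 60 clinical staff could come from max(30, 30) = 30 events. With disjoint frames they need 30 + 30 = 60.
3. Section 6.1 says that the number of events may exceed 30 because not everyone will be involved in any one event. That wording fits an expectation of overlap between the two staff groups. The invitation rule rules such overlap out.

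The 30 and 60 rest on the one-per-event assumption. Interviewing several colleagues from one event would lower both numbers, but the intersections would stay empty.

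**The case against.** The strongest reply is that linkage is an aim and not a condition. Section 6.1 says that it will not always be achieved. Section 6.4 accepts that some events will have a single source and compares between events as well as within them. The thematic and ethical analyses need no linked events, and the transport and ED stages can be coded from ED and survivor accounts. All of this stands, and it limits the consequence. It does not remove the contradiction: the qualifier describes incomplete recruitment, whereas for paramedic–ED and paramedic–survivor pairs the written rule allows none at all.

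A reader might infer that the whole same-event comparison is impossible. The documents do not support that, because two pairings survive.

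A reader might also infer that paramedics who transport patients are never heard. That goes too far as well. A paramedic invited through a ROLE case may have transported other patients. Section 6.2 asks about cardiac arrest more generally, and the vignettes described in Section 6.1 cover decisions to continue as well as to stop. What is missing is the account of an index transported event by the crew who attended it.

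It is also tempting to size the gap by the national share of patients transported, from Section 1.1. Those annual counts do not measure harm in a qualitative sample that runs to saturation and claims no proportional representation.

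Finally, Figure 2 (Recruitment of Participants) is not shown in the copy reviewed, and Sections 2.3 and 2.4 define eligibility simply as ambulance staff. The intended design may therefore be wider than the paragraph. If Figure 2 shows another route, it conflicts with the text and the two still have to be reconciled.

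**Conclusion.** The point holds in limited form. As Section 6.1 is written, no event can give a paramedic–ED, paramedic–survivor or three-way comparison, although Sections 6.1 and 6.4 plan for comparison across these groups. Up to 30 ambulance interviews are recruited under this rule. Paramedic–bereaved relative pairs and ED–survivor or ED–relative pairs are unaffected.

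The conclusion assumes that the index-event paragraph is the operative invitation rule and that Figure 2 adds no further route. It also sets aside the chance that a paramedic invited through a ROLE case happens to have attended a transported event under study, since no procedure is given for linking such accounts.

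This should be fixed, but it does not endanger the study. It concerns one qualitative work package, no quantitative estimate depends on it, and the other WP4 analyses can proceed.

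**What to change.** Amend the ambulance-staff paragraph of Section 6.1 so that the research paramedic also identifies and invites paramedics who attended cases transported to a participating ED, linked to the events for which ED staff are identified. Keep the existing maximum of 30 ambulance interviews. Reconcile Figure 2 with the revised text.

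If the sponsor prefers to keep the present frames, the alternative is to withdraw the paramedic–ED and paramedic–survivor same-event aim from Sections 6.1 and 6.4 and to say which pairings the event analysis will use.

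The first option needs a short protocol and ethics amendment. The research paramedic already follows non-ROLE cases to three months, so these events are known to the ambulance service and no extra interviews are required. The price is fewer ambulance interviews per event type. The second option needs only a text change, but gives up the comparison between pre-hospital and hospital clinicians on one event.

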6.2 Data collection for WP4

Data collection: Interviews will be similarly structured, but modified by stakeholder panels, to address:

- The experience of the cardiac event what happened, where, when, who was there, what they did, what happened afterwards
- Their reflections on the event expectations, dilemmas, challenges, values and beliefs
- What would they want others to learn from the event?
- Exploration of attitudes, beliefs and preferences about cardiac arrest more generally, prompted by vignettes developed with input from our expert advisory group and PPI advisory group.

Interviews with family members who were not present will cover the same topics and we will ask them about the source of what they know about the event. Interviews will be carried out face to face or remotely, if preferred by the participant or necessary due to COVID-19 restrictions. To ensure that confidentiality is maintained, face to face interviews will be held at a mutually agreed, suitable location. Remote interviews will be carried out via telephone or using an online communication platform, such as Microsoft Teams, at a mutually agreed time. Informed consent will be obtained prior to interview. Consent will be written where interviews are face to face and audio-recorded where held remotely via telephone or using an online communication platform such as Microsoft Teams. Interviews will usually last for clinicians, up to 40 minutes and for survivor/relatives, up to an hour. Interviews will be transcribed verbatim, transcripts checked and imported into NVivo.

All participants will be offered a shopping voucher (LOVE2SHOP) worth £40, in consideration of their time to take part in the interview.

6.3 Data management for WP4

Personal data will only be held following verbal consent and kept in order to facilitate the arrangement of the interviews. The data will be kept on password control encrypted spreadsheets and stored in a secure area of the computer with access restricted to staff working on the study.

Audio recordings will be transcribed and anonymised. All qualitative data will be uploaded into appropriate software which will be used to assist data management. Audio recordings will be transferred from site to the University securely using encryption either on the audio recorder, or by downloading the recording to an encrypted laptop. The recordings will be transferred to secure university servers for secure storage and copies on the audio recorder and/or laptop deleted. Transfer to any transcription services will be done via a secure system and according to Warwick data transfer SOPs and a contract with a UoW approved transcription service provider. Hand written field notes will be kept in a locked filing cabinet. Field notes recorded electronically will be on an encrypted laptop while the researcher is at the site and then uploaded to secure university servers when they return to the office.

6.4 Data analysis for WP4

Data quality checks: all qualitative transcriptions will be checked against the initial interview recording to ensure consistency. A record of these checks will be logged and reported back to the SMG. SMGs will also evaluate interpretations made from the data.

Data analysis: Analysis will be undertaken as follows:

- Comparative analysis of data related to cardiac events⁷⁵ Data about any one event will be grouped (although sometimes we may only have one data source for an event). From analysis of initial data we will develop an event pathway. This is likely to be before event, arrival at event, assessment, active treatment, evolving the decision to terminate or not, transport, ED activity, post ED. Data will be coded to stages in the pathway. To understand the diversity of experience and the reasons for this diversity, we will compare data from different stakeholders about the same event at the different stages and between events.
- *Thematic analysis*⁷⁶ This analysis will focus on data on expectations, dilemmas, challenges, values, attitudes, beliefs and preferences wherever it occurs in the data. Transcripts will be coded close to
text, with codes summarising the coded text. Codes will then be sorted and categorised into themes to provide a rich description of the range of perspectives and how these influence decisions and actions at cardiac events.

Descriptive ethical analysis⁷⁷ This involves interpreting and evaluating the ethical or moral dimensions
of the reality reported in the interviews. Working with our ethicist we will re-read interview
transcripts looking for explicit and implicit ethical concerns for those encountering cardiac arrest in
their work/life and the values they express or imply related to cardiac arrest. During analysis we will
relate these to current ethical, legal and professional frameworks.

Each analysis will result in a report to inform the normative ethics review and consensus conference.

Normative ethical analysis: Findings from all work packages will be considered together with other relevant literature both empirical and theoretical on decision-making around termination of resuscitation, ethical theory and current regulatory frameworks. We will use the process of bioethical enquiry known as reflexive balancing to analyse the normative question of when should resuscitation attempts be terminated and what rules should govern these decisions. This entails identifying and then balancing as far as possible, the range of relevant concerns, interests and priorities that operate on an ethical problem and suggest a coherent compromise.⁷⁸ A report of this analysis will feed into the consensus conference discussions.

